5 CORRELATIVE STUDIES FOR RESEARCH

5.1 BIOSPECIMEN COLLECTION

This study will attempt to use rhIL-15 to increase NK cell number and activity, thereby enhancing the ADCC of avelumab in treatment of patients with relapsed and refractory mature T-cell malignancies. ADCC capacity of ex vivo PBMCs will be tested on PD-L1-expressing cell lines before, during and after protocol treatment. Differences in immune cell subsets associated with administration will be followed throughout treatment to both study the effects of combined rhIL-15/avelumab therapy on the immune system, and to identify potential biomarkers that would be predictive of response.

Sample	Collection Details*	Time Points									Supervising Laboratory/Investigator
		Baseline	C1 D5	C1 D8	C1 D9	C1 D22	C2-6 D1	C2-6 D8	Follow-up [#]		
Blood Samples											
Lymphocyte subset testing	• 2 x 10mL K ₂ EDTA (lavender-top) tubes	X		X		(X)	(X)	(X)	(X) ¹	Immunology section, NIH CC	
ADCC of avelumab	• 3 x 10mL sodium heparin green-top tubes	(X) ²		(X) ²	(X) ²			(X) ²		[name]	
Tissue immune cell subsets (comparison)	• 1 x 5mL green-top tube	(X)				(X)			(X)	[name]	
PBMC Banking	• 3 x 10mL sodium heparin green-top tubes	X	(X)	X		X	X	X	(X)	[name] (Leidos CSL)	
Circulating tumor DNA, plasma banking	• 1 x 10mL K ₂ EDTA tube • 1 x 10mL Streck/BCT tube	X		(X)				(X)	X ³		
Anti-IL-15 antibodies	• 1 x 4mL SST tube	X					X		X ¹		
Tissue Samples											
Tissue immune cell subsets	• Two core biopsy samples in RPMI 1640 with 10% human serum and antibiotics • One core biopsy sample in formalin NOTE: Samples may be tumor tissue or bone marrow aspirate/biopsy	X**				(X)			(X)	[name]/(RPMI 1640) and DLM/NCI LP (formalin)	
Other Samples											
Germline DNA	• Blood, Buccal Swab, or Saliva (preferred)	X								[name]	
	(X) = Optional; samples will be collected if adequate time/staff available for processing. If an optional sample is not collected at baseline, it would also not be collected in follow-up unless specifically requested by the PI.										
	*Tubes/media may be adjusted at the time of collection based upon materials available or to ensure the best samples are collected for planned analyses.										
	** Tumor biopsy is required if archival tissue is not available or adequate; otherwise, this is optional										
	#Subjects who discontinue treatment for a reason other than disease progression and who do not start new treatment should continue to have study bloods collected at the scheduled time points.										
	¹ At the end of treatment only.										
	² For ADCC of avelumab, Baseline and C1D8 samples should be collected for at least one patient per dose level, and for at least three patients at the MTD; C1D9 and C2-6 samples may be collected at the discretion of the PI, but are not required.										
	³ At each follow-up visit prior to disease progression, as specified in Section 3.5.3.										

5.2 SAMPLE COLLECTION AND PROCESSING

5.2.1 Summary

The planned analyses described below may be done on leftover and/or shared sample portions from the respective laboratories, as needed. In addition to the prospectively collected samples below, leftover portions of samples sent for routine laboratory testing (e.g., plasma from CBC/hematologies) may also be retrieved for research tests prior to being discarded. The planned prospective analyses are identified below; laboratories may share resources or collaborate on analyses, if appropriate.

Portions of all samples may be banked for future research analyses; prospective consent will be obtained during the informed consent process.

The blood drawing limits for research purposes are as follows:

- For adult subjects: The amount of blood that may be drawn from adult patients for research purposes shall not exceed 10.5 mL/kg or 550 mL, whichever is smaller, over any eight-week period.

All samples will be delivered to the laboratory of [name], Lymphoid Malignancies Branch. The laboratory staff will handle processing or delivery/shipping of associated labs, if applicable. To arrange for sample processing, contact: [name], Lymphoid Malignancies Branch ([name]; [contact]) or [name]., Lymphoid Malignancies Branch ([name]; [contact]). Tissue samples will also be sent to the Hematopathology Section of the National Cancer Institute Laboratory of Pathology, by courier service.

5.2.2 Blood Samples

All blood samples will be drawn by NIH Clinical Center phlebotomy, inpatient unit, outpatient clinic, or day hospital staff

5.2.3 Lymphocyte subset testing by flow cytometry (FACS)

- Collect blood in EDTA tubes; gently invert tubes 8-10 times immediately after collection
- Labels listing the patient's name, date of birth, date and time of the blood draw will be affixed to all the tubes by the staff person who obtained the samples.
- Lymphoid Malignancies Branch Clinical Research personnel will arrange for these samples to be delivered to: Immunology Lab, NIH Clinical Center [name]. If the Immunology Section Laboratory is unable to perform this analysis on the specified days, this assessment maybe omitted or replaced with standard TBNK panel

5.2.4 Antibody-dependent cell cytotoxicity (ADCC) of avelumab

- Collect blood in sodium heparin tubes; gently invert tubes 8-10 times immediately after collection.
- Samples will be processed per established laboratory techniques.
- Lymphoid Malignancies Branch Research personnel will arrange for these samples to be delivered to Clinical Support Laboratory, Leidos Biomedical Research, Inc. in Frederick, MD, for storage and further analysis, or directly to [name] for immediate analysis.

5.2.5 Cell-free DNA (cfDNA), and circulating tumor DNA (ctDNA) and plasma banking

- Collect 10 mL of blood in one cell-free DNA (e.g., Streck BCT/collection tubes) and 10 mL of blood in one K2EDTA tube; gently invert the tubes 8-10 times immediately after collection.
- Labels listing the patient's name, date of birth, date and time of the blood draw will be affixed to all the tubes by the staff person who obtained the samples. Plasma will be isolated and frozen at -80°C until analysis (e.g., centrifuged at 1800 x g for 10 minutes at room temperature; plasma transferred/frozen in aliquots of 1.5-2 mL each).
- Lymphoid Malignancies Branch Clinical Research personnel will arrange for these samples to be delivered to Clinical Support Laboratory, Leidos Biomedical Research, Inc.in Frederick, MD for sample processing per established techniques maintained within standard operating procedures in the laboratory.

5.2.5.1 Anti-IL-15 antibody testing

- Collect blood in a 4mL SST tube; gently invert tubes 8-10 times immediately after collection.
- Lymphoid Malignancies Branch Research personnel will arrange for these samples to be delivered to Clinical Support Laboratory, Leidos Biomedical Research, Inc.in Frederick, MD, for storage and further analysis.
- Samples will be batch processed and analyzed per the procedure outlined in **APPENDIX E** after the last patient has been enrolled and completed treatment, or sooner if there is clinical suspicion for anti-IL-15 antibody formation.

5.2.5.2 PBMC Banking

- Collect blood in sodium heparin tubes; gently invert tubes 8-10 times immediately after collection.
- Lymphoid Malignancies Branch Clinical Research personnel will arrange for these samples to be delivered to Clinical Support Laboratory, Leidos Biomedical Research, Inc.in Frederick, MD for sample processing per established techniques maintained within standard operating procedures in the laboratory.

5.2.6 Tissue Samples

5.2.6.1 PDL-1 testing for immunohistochemistry (IHC)

- Archival block(s) or slides (i.e., at least 15 unstained slides, 5-microns) is required at baseline. Patients with prior skin, lymph node, or visceral biopsies performed at NIH or outside institutions must make specimen blocks available to the NCI Pathology Department for analysis. If no prior biopsies are available at the time of screening, patients with Cutaneous T-cell lymphoma and other lymphoma with skin involvement will undergo a punch biopsy of a skin lesion, performed by an NIH Clinical Center dermatologist. Patients with lymph node and/or visceral involvement will undergo an 18g core biopsy performed by the Department of Radiology and Imaging Sciences' Interventional Radiologists (IR). An optional biopsy may be performed in the same manner prior to the second dose of avelumab (Cycle 1, Day 22).
- Prior specimen blocks will be sent to NCI Pathology Department via Fedex. For patients with no prior samples who undergo biopsy as part of screening (if needed for diagnosis) or baseline, core tumor tissue (or bone marrow aspirate/biopsy) samples will be collected and

placed in appropriate media (e.g., RPMI 1640 with 10% human serum and antibiotics, and formalin) and processed per established techniques. As indicated (Sections **5.1** and **5.2**), samples will be sent to the Department of Laboratory Medicine (DLM)/ NCI Laboratory of Pathology (LP) for concurrent routine histologic analysis and reporting and IHC testing for PD-L1 expression by tumor cells and tumor-associated immune cells in addition to research testing (i.e., [name] Lab).

5.2.7 Other Samples

5.2.7.1 Germline DNA

Germline DNA will be collected by blood, buccal swab, and/or saliva samples (preferred). These will ideally be collected at baseline; however, may be collected at any point on study based on supplies. Standardized, commercial collection kits or tubes will be used (e.g., 1, 5-10 mL K₂EDTA tube for blood; Isohelix SK-1 for buccal swabs; Salviette/Oragene® for saliva). In the case of buccal swabs, two (2) samples may be collected in order to ensure adequate DNA collection.

The samples will be processed and DNA extracted/isolated per kit instructions and established techniques.

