2 ELIGIBILITY ASSESSMENT AND ENROLLMENT

2.1 ELIGIBILITY CRITERIA

2.1.1 Inclusion Criteria

2.1.1.1 Patients must have histologically or cytologically proven relapsed/refractory T-cell lymphoma other than adult T-cell leukemia/lymphoma (ATLL), angioimmunoblastic T-cell lymphoma (AITL), peripheral T-cell lymphoma T follicular helper phenotype (PTCL-TFH), or enteropathy-associated T-cell lymphoma (EATL), confirmed by the Laboratory of Pathology, NCI

2.1.1.2 Patients with CD30+ mycosis fungoides/Sézary syndrome (MF/SS) or CD30+ anaplastic large cell lymphoma (ALCL) must have relapsed after or become intolerant to treatment with brentuximab vedotin.

2.1.1.3 A formalin fixed tissue block or 15 slides of tumor sample (archival or fresh) must be available for performance of correlative studies. **NOTE:** Patients must be willing to have a tumor biopsy if prior tissue or adequate archival tissue is not available (i.e., post-enrollment and prior to treatment).

2.1.1.4 Disease must be measurable with at least one measurable lesion by RECIL 2017 or mSWAT criteria (see Section [6.3](#)), or have an abnormal clonal T-cell population detectable by peripheral blood flow cytometry

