2.4.5 Research Correlates

NOTE: See Section 5 for additional information. The following sample types will be collected for correlative research studies:

[figure not shown]
- Required:
 - Blood samples for lymphocyte subset testing and circulating tumor DNA
 - Blood, buccal swab, or saliva for germline DNA
 - Tumor Tissue (archival or fresh)

- Optional:
 - Blood samples for ADCC of avelumab, tissue immune cell subset comparison (as outlined in Section 5.1)
 - Bone marrow biopsy
 - Tumor biopsy is required if archival tissue is not available or adequate; otherwise, this is optional.

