⁹ Physical exams to include medical history (i.e., complete at Screening/Baseline; interim on study and in follow-up), vitals, weight, and height (screening only). ECOG to be recorded at least once per cycle, on day 1, 8, and/or 22.

¹⁰ Chemistry panels include: Acute care, Hepatic, and Mineral.

¹¹ Diffusing capacity/alveolar volume (DLCO/VA), forced expiratory volume in 1 second (FEV1) for patients with significant pulmonary or smoking history.

¹² At screening a CT scans of neck, chest, abdomen, and pelvis should be performed (with IV and PO contrast, unless patient is allergic or has renal insufficiency; other imaging may be substituted at the discretion of the investigator). Other body areas may be imaged if clinically indicated. MRI of the brain is only required in patients with suspected involvement of CNS. Also, at screening, a FDG-PET/CT torso (extremities to be included if there is confirmed or suspected disease involvement). At baseline one or more of the following studies: CT, MRI, FDG-PET/CT and or clinical photography.

¹³ Patients with neurological symptoms or signs should undergo MRI scan of the brain and lumbar puncture.

¹⁴ Baseline bone marrow aspiration/ biopsy with flow cytometry must be done within 3 months prior to starting treatment. During post-treatment follow-up, repeat bone marrow aspiration/ biopsy needed only to confirm a CR.

¹⁵ Peripheral blood flow cytometry may be done for disease evaluation of patients who had circulating leukemic cells detected at baseline, and for patients with CTCL regardless of their baseline results.

¹⁶ To be performed in selected patients with cutaneous disease (as determined by PI or AI).

¹⁷ Dermatology assessment and Global/mSWAT scoring will be used instead of or in addition to radiologic evaluation for patients with predominantly cutaneous disease

¹⁸ Samples for correlative research are to be collected as indicated in Section 5. Prior biopsy specimen blocks will be used for PD-L1 staining if available. If archival tissue is not available or adequate, baseline punch biopsy of the skin or core needle biopsy of a lymph node/visceral lesion is required, otherwise this is optional.

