5.3.3 ADCC Analysis

Peripheral blood mononuclear cells (PBMCs) should be isolated by Ficoll-Hypaque Density Gradient Centrifugation. The viable cells should be viably frozen and stored in liquid nitrogen. The ADCC assay will be performed on the same occasion for all samples of a given patient. Vials of frozen cells will be thawed using standard procedures 18 hours before the assay in accord with our experience with normal donors. 1.5 million of patient's PBMCs obtained before and on day 15 following IL-15 injection will be tested in aliquots as follows:

- Tested alone

- Tested with untreated PD-L1-expressing Raji cells, and with the Raji cells coated with avelumab for 5 hours.
- In addition, we may utilize an ATL cell line in addition to Raji cells. These cell populations will be stained with CD107, CD3, CD56, and CD94.

5.3.4 cfDNA/ctDNA and PBMC banking

Since the methods of molecular monitoring in the peripheral blood is an emerging field with numerous technologies under development, the storage of peripheral blood mononuclear cells (PBMC), serum, and plasma will all be performed allowing for future comparison of the different compartments for analytes that include cell-free circulating tumor DNA (ctDNA), and RNA sequencing of circulating tumor cells. Studies to be performed on these samples include: cfDNA/ctDNA for liquid genotyping as a non-invasive dynamic monitoring of disease as well as monitoring for individual molecular aberrations that herald progression or disease transformation; specifically, amplification and sequencing of the VDJ segment of the immunoglobulin receptor is planned. Germline DNA obtained from saliva, blood, or buccal mucosa will be used to discriminate somatic from germline mutations during cfDNA and ctDNA analyses. Keeping in mind a recent report of immune checkpoint inhibition in a patient with a solid tumor being associated with T-cell lymphomagenesis (50), and with our own group's experience with rapid progression in 3 patients with ATLL treated with ICI (22, 51), special attention will be paid to following T-cell clonality using amplification and sequencing of the complementarity determining region 3 (CDR3) in both cfDNA and banked PBMCs.

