5.3.5 DNA/RNA Sequencing

Genomic DNA and total RNA will be extracted from tumor samples using a Qiagen All-prep kit. For individual target genes that are recurrently mutated in T-cell malignancies, classical Sanger sequencing will be performed on PCR amplicons, using primers surrounding the known sites of mutation. To broadly assess mutations, next generation sequencing (e.g., on an Illumina HiSeq 2000 platform) will be employed, using a paired end sequencing strategy of libraries constructed from tumor DNA. DNA will either be sequenced in its entirety from a whole genome library or will be first enriched for exonic sequences using the Agilent Sure Select system, aiming for 30X or 100X average coverage per base, respectively. The sequence fragments will be mapped back to the genome using the BWA algorithm. Of sequences overlapping a particular base pair in the genome, the percent mutant calls greater than 20% with a minimum of 25X coverage will be considered as an arbitrary threshold for single nucleotide variants (SNVs). SNVs that are not present in the matched normal sample will be considered candidate somatic mutations.

A related technology, RNA-Seq, utilizes RNA from the tumor specimen to create a cDNA library for high-throughput sequencing. RNA-seq will be performed using Illumina kits followed by high-throughput sequencing on an Illumina HighSeq 2000 machine. The cutoffs for coverage and percent mutant calls mentioned above will also be used to identify putative SNVs. RNA sequencing will also be used to read out digital gene expression across the genome as described.

Recent advances in genomic technologies enable GEP at the single cell level, a distinct advantage over conventional GEP which cannot always distinguish tumor vs non-tumor gene expression. Single-cell approaches allow identification of the evolution of rare populations of resistant tumor cells, as well as identification of TME cells critical for the survival of the tumor. The Center for Cancer Research (CCR) has recently opened a single cell analysis core facility with expert staff headed by [name] within the CCR Genomics Core. This facility has the ability to take

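### Blood may serve as the germline control even in patients with a circulating T-cell clone; where it does, the somatic filter can remove true tumor SNVs

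*Combined protocol and SAP*

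**What the plan says.** Four places define the germline control, and each accepts blood:

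- Section 2.4.5 lists "Blood, buccal swab, or saliva for germline DNA" and states no preference.
- The sample table in Section 5.1 and the text of Section 5.2.7.1 mark saliva as preferred. The latter reads "Germline DNA will be collected by blood, buccal swab, and/or saliva samples (preferred" and adds that the sample "may be collected at any point on study based on supplies".
- Section 5.3.4 gives the purpose: "Germline DNA obtained from saliva, blood, or buccal mucosa will be used to discriminate somatic from germline mutations during cfDNA and ctDNA analyses".

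None of them excludes blood when the blood is involved by lymphoma. None asks for tumor-cell depletion, sorting or a contamination check.

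Blood involvement is foreseen. Section 2.1.1.4 accepts, as an alternative to a measurable lesion, patients who "have an abnormal clonal T-cell population detectable by peripheral blood flow cytometry". Mycosis fungoides/Sézary syndrome is a named subgroup in Section 10.4.7. Footnote 15 of the Study Calendar (Section 3.6) says "Peripheral blood flow cytometry may be done for disease evaluation of patients who had circulating leukemic cells detected at baseline".

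The somatic filter is in Section 5.3.5: "SNVs that are not present in the matched normal sample will be considered candidate somatic mutations". The sentence before it sets a calling threshold of more than 20% mutant calls at 25X or deeper, and does not say whether that threshold also applies to the normal.

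**The concern.** A germline control is useful only if it is free of tumor. In a patient with a circulating clone, DNA from whole blood is a mixture of normal and malignant genomes. A filter that discards any variant found in that mixture discards some of the patient's own tumor mutations.

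The error runs in one direction, because true mutations are removed and none are added. It falls on one kind of patient, those with leukemic or Sézary disease. Molecular correlates based on SNVs could then look sparse in that group because of how the control was sampled. The same control is meant to separate somatic from germline variants in cfDNA, so SNV-based work there is exposed as well.

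**Working it through.** The plan gives no figure on this point, so there is none to reproduce. The check asks how likely it is that a true tumor SNV is found in a blood control and therefore filtered out.

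**Inputs from the documents**
- Average coverage of 30X (whole genome) or 100X (exome), Section 5.3.5. The text gives these depths when describing tumor libraries; I assume the same depth for the normal.
- SNV threshold of more than 20% mutant calls, Section 5.3.5.

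**Assumptions**
- f, the tumor share of nucleated blood cells, is not given; it is varied from 5% to 60%.
- The SNV is clonal, heterozygous and diploid, so its expected allele fraction in blood DNA is f/2.
- Sequencing error is ignored.
- The matched normal in Section 5.3.5 is the germline sample of Section 5.2.7.1. The text does not say so outright, but it describes no other normal.

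**Formula.** With depth n, the number of mutant reads X in the normal is Binomial(n, f/2). The SNV is lost if X reaches the count r that makes it present. Three readings of present are used:
- at least one read, r = 1, so P = 1 − (1 − f/2)^n;
- at least two reads, r = 2;
- more than 20% of reads, r = 7 at 30X and r = 21 at 100X.

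**One-read rule with numbers in**
- f = 5%, 30X: 1 − 0.975^30 = 0.532
- f = 5%, 100X: 1 − 0.975^100 = 0.920
- f = 10%, 30X: 1 − 0.95^30 = 0.785
- f = 10%, 100X: 1 − 0.95^100 = 0.994

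**Probability that a true SNV is filtered out, 30X / 100X**

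| f | at least 1 read | at least 2 reads | more than 20% of reads |
|---|---|---|---|
| 5% | 53% / 92% | 17% / 72% | about 0 / about 0 |
| 10% | 79% / 99% | 45% / 96% | about 0 / about 0 |
| 20% | 96% / >99% | 82% / >99% | 3% / 0.1% |
| 30% | 99% / >99% | 95% / >99% | 15% / 7% |
| 40% | >99% / >99% | 99% / >99% | 39% / 44% |
| 60% | >99% / >99% | >99% / >99% | 84% / 98% |

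With a tumor-free normal (f = 0) the loss from this mechanism is zero. How *present* is defined therefore moves the result as much as f does: at f = 10% it takes the loss at 100X from 99% to about 0.

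**The case against.** The strongest reply is that the harm needs three things together: a patient with a circulating clone, blood actually used as the control, and a strict reading of the filter. Saliva is marked as preferred, and the freedom to collect late also lets staff wait for a saliva kit instead of falling back on blood. Among at most 30 patients, the number affected could be zero. The 20% threshold stands immediately before the filter sentence and may well be meant to govern the normal too; on that reading, little is lost below roughly f = 40%. The introduction to Section 5.3 says methods will be settled, and the protocol amended if needed, when samples are ready for analysis. Section 5.3.5 calls its threshold arbitrary and its output candidate mutations. Somatic calling appears in no primary or secondary endpoint.

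Much of this stands. The problem is conditional, its frequency is unknown, and its size cannot be narrowed beyond the table. The filter rule could be settled later. The sample source could not: a later amendment cannot remove tumor DNA from a control already collected, and a patient who has died or left the study cannot be resampled. A preference with no exclusion does not prevent this.

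A reader might also infer that ctDNA monitoring is lost in leukemic and Sézary patients. The documents do not support that. Section 5.3.4 specifies VDJ sequencing and CDR3-based tracking of T-cell clonality, and neither depends on subtracting germline SNVs. The Sanger sequencing of recurrently mutated genes in Section 5.3.5 is not described as subject to the matched-normal filter.

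**Conclusion.** The point holds as a conditional one. The plan allows a blood germline control in patients known to have a circulating clone, and when that happens the filter as written can delete true somatic SNVs. SNV-based separation of somatic from germline variants in cfDNA shares the weakness.

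It would be tempting to quote losses of 53% to 99% as the expected effect. The documents do not support that either, because those figures need a one-read meaning of *present* that is stated nowhere and a value of f that is not given. The supportable statement is a range: from about 0 at f = 10% under the 20% rule to nearly complete loss at f = 10% and 100X under the one-read rule. Under the 20% rule the loss becomes large from about f = 40%.

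The effect is confined to correlative sequencing. The MTD, DLT assessment, safety, response and survival endpoints are unaffected, as are PD-L1 expression, ADCC, clonotype tracking and the sample size.

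**What to change.** 1. In Sections 2.4.5, 5.1, 5.2.7.1 and 5.3.4, require a non-blood germline source for any patient with a circulating clone on screening or baseline blood flow cytometry. The buccal and saliva kits already listed would serve. Blood flow cytometry is the safer trigger: T-cell receptor PCR is also done at screening, but neither Section 2.2.3 nor the Study Calendar states its specimen.
2. In Section 5.3.5, for these patients, replace the requirement of absence from the normal with a rule that the tumor allele fraction must significantly exceed the fraction in the normal. This is needed even with a non-blood control, because saliva and buccal samples may carry leukocytes.

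The cost is mainly wording. Blood is lost as a fallback source in these patients, and some leukocyte carry-over may remain, which the second change is meant to tolerate.
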